39.1 Quantitative analyses

The flow of participants through the trial will be detailed in a CONSORT flow diagram. The number of people screened, randomly assigned, receiving the intervention, completing the study protocol and providing outcome data will be summarised overall and by trial arm. The number of individuals withdrawing from the intervention and/or the trial and any reasons for withdrawal will be summarised by trial arm. To quantify the acceptability of the intervention the number of sessions attended will also be summarised. All data will be presented descriptively with no formal statistical analyses undertaken. For each data collection point and outcome measure, the number of nonresponders will be calculated and completion rates compared. The potential impact of therapist effects may be explored using ICC and the average caseload per therapist will be detailed.

40. Analysis of economic and quality of life data

The economic component of the study will be designed to assess the feasibility of conducting a cost-effectiveness analysis of a full trial. This will involve piloting a short questionnaire, analysing responses and calculating Quality Adjusted Life Years (QALY) changes using the EQ-5D. We would not expect to see significant changes between groups due to the small sample size in this feasibility trial.

A simple questionnaire will measure participants' use of health care and will be identified retrospectively by means of service use questions. The economic analysis will assess the feasibility of using such a questionnaire in this population. The questionnaire will ask about primary care, sexual health and family planning services. In the full trial resource use data will be multiplied by national average unit costs to calculate per participant costs in the 3 month period before the intervention and the 3 month period after receiving the sexual health intervention or TAU.

Quality of life will be measured by EQ-5D at baseline and each follow up time point. The use of EQ-5D enables the estimation of QALYs. Measuring health status using QALYs follows the recommendations of NICE¹ and enables the value for money afforded by treatments to be compared to a range of other health care interventions.

A full cost-effectiveness analysis will not be conducted in this feasibility trial. The economic component of this trial will examine the feasibility of conducting a full incremental cost-effectiveness analysis of sexual health intervention compared to TAU. This feasibility trial will inform the choice of appropriate effectiveness measure for the economic analysis and aid the identification of relevant resource use categories.

41. Compliance and withdrawal

41.1 Participant compliance

Participants will not be withdrawn on the basis of non-compliance with the intervention.

41.2 Loss to follow up

The RESPECT team will contact the participant's case manager or GP to identify any new contact details for a participant who we have lost contact with.

41.3 Withdrawal/ dropout of participants

Participants may withdraw from the study at any time without influencing their future care or treatment. Withdrawal may refer to the following situations:

- Where a participant wishes to withdraw from the study intervention, but is
 prepared to continue completing follow-up questionnaires (i.e. no intervention
 sessions are attended but the data is still collected). This is classed as
 'Withdrawal from intervention'. This is pertinent only to the sexual health
 intervention arm of the study.
- Where a participant wishes to withdraw from completing any further follow-up interviews after completing their intervention sessions. This is classed as 'Withdrawal from follow-up'. This is applicable to both arms of the study.
- Where a participant wishes to withdraw from both the study intervention AND from completing any further follow-up interviews. This is classed as 'Full withdrawal'. This is applicable to both arms of the study.
- A person can be withdrawn without their consent from the intervention and/or the trial for reasons of risk or harm to self and/or others. This would only be actioned with evidence of serious and significant risk. In these instances the risk protocol will guide the interventionist and/or researcher in the appropriate action to be taken in conjunction with the lead research clinician and the duty worker in the organisation.

• We will ensure that the researchers are aware of the differences in types of withdrawal, and that they are explicit about whether participants wish to withdraw from the intervention, follow up, or both.

In either event, York Trials Unit will be informed.

42. Interim analyses

No interim analyses will be conducted.

43. Data Monitoring

The Chief Investigator will ensure that the study is appropriately monitored by ensuring that: all rights of the trial participants are adequately protected; that written informed consent is obtained; the trial data are accurate and complete; and that the conduct of the trial is in compliance with the protocol and its subsequent amendments, with GCP and applicable regulatory requirements.

44. Training

The intervention will be manual based, and the intervention manual will be adapted in accordance with the current trial. There will be a two day training session to introduce staff to the key-concepts and procedures involved in the intervention and research. In addition, we will create a private learning space within the University of Huddersfield online learning platform (UniLearn) for the interventionists. Within this secure space, interventionists will be able to access remotely and securely all the resources to support the delivery of the intervention as well as the manual, forms and exercises.

Once the trial commences, supervision will be provided on a regular on-going basis via monthly 'supervision' phone meetings with the CI. The clinician will also be able to contact the CI between scheduled sessions for advice and support.

45. Ethical considerations

45.1 Regulatory approvals

The proposed study will be conducted in accordance with the MRC Guidelines on Good Clinical Practice in Clinical Trials. Prior to undertaking the study, approval will be sought from the Health Regulatory Authority and local Research and Development department.

45.2 Informed consent

All eligible people with SMI will be provided with a PIS prior to giving consent. The information sheet will outline fully the potential benefits and risks of being involved in the trial. This information sheet will meet all the requirements of the HRA. Maintenance of confidentiality and compliance with the UK Data Protection Acts will be emphasised to all study participants. Participation in the study will be entirely voluntary and written consent will be sought. All data will be treated with the strictest confidence. Potential participants will be excluded from participating in the trial if it is felt they are lacking in capacity to consent as guided by the Mental Capacity Act.

45.3 Risks and anticipated benefits for trial participants and society

The main risk from participating in the study is embarrassment regarding collecting data about sexual behaviour, and if receiving the intervention, discussing sexual health and relationships. In order to minimise this, potential participants will be informed of the specific nature of the study prior to consent. The research will be undertaken in a sensitive way, maintaining awareness of the vulnerability of many of the participants.

In terms of benefits to society, should this new intervention prove clinically and cost effective in a larger, multi-site trial and should it be widely implemented, it would have a significant impact on the sexual health of people diagnosed with SMI. The aim is to design and trial a realistic intervention that can be readily delivered even in a climate of cuts for treatment services. The scope for implementation and impact is therefore great.

46. Safety and Adverse events

There are no anticipated risks in relation to either arm of the trial. However, the research team are aware that some people who have experienced sexual abuse and exploitation may find participating in this study distressing and may trigger difficult feelings.

Distress management – if a participant expresses any signs or reports any distress during any study related activity (e.g. meeting with a member of research team or during intervention delivery) an immediate halt will be implemented to the activity. Study specific guidance will be used to guide the researcher or interventionist for the management of this situation. Incidences of low level distress will be reviewed during scheduled supervision meetings. If a participant is referred to the local mental health team for management of their distress the CI (or delegated research clinician) will be informed within 24 hours.

Adverse events – If a participant becomes unwell during the course of the study (irrespective of condition) and needs to be admitted as an inpatient or other adverse event occurs (self-harm, suicide attempt, violence to others or victim of violence) this will be reported to the CI (or delegated clinician) immediately on receipt of this information, and the chair of the DMEC within 48 hours. The Chair of the DMEC will have the authority to terminate the trial should there be evidence that the study is causing harm.

All adverse events (AE) [serious and non-serious] will be reported to the Chief Investigator and reviewed by [name] who is a clinical psychologist and experienced health researcher at the University of Huddersfield according to a Standard Operating Procedure (SOP) specific to this study. We are aware that judgements regarding relatedness can be difficult in this type of study, and therefore all serious adverse events (SAE) will be forwarded to the DMEC within 48 hours of the CI becoming aware of the event. Any event deemed by the team and the DMEC as 'related' to study treatment will be reported to the sponsor, ethics committee and TSC. Any non-serious

47. Project management

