23.1 Level of blinding

By the nature of the interventions used within this study, blinding of the participants, clinicians and the researchers is not possible. However, those involved in the analysis of the data will be blind to treatment allocation.

24. Measures to avoid/ minimising bias

Potential sources of bias will be minimised by having minimal exclusion criteria, randomisation, standard training of clinicians guided by a treatment manual, measures of treatment fidelity and adherence to the manual, validated outcome measures and an intention to treat analysis.

25. Data collection

All information collected during the course of the trial will be kept strictly confidential. Information will be held securely in paper format at York Trials Unit, University of Huddersfield University College London and within the R&D departments of each participating Trust and electronically at York Trials Unit. All trial data will be identified using a unique trial identification number. Analytical datasets will not contain any identifiable information. Data will be archived for a period of 5 years following the end of the study.

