47.4 Data Monitoring and Ethics Committee (DMEC)

The committee will consist of independent experts (including independent statistician and mental health professionals, who are independent of the principal investigator and the study team. Its remit will be to monitor the trial data in particular quality control and quality assurance of the data collected and progress of the trial including adherence to the trial protocol. The committee will also examine and ensure that the dignity, rights, safety and wellbeing of all study participants are maintained at all stages of the trial. Data reports will be supplied, including any adverse events, and the committee will have access to summary data and documentation. The Chair of the DMEC will be informed of any adverse events that arise from the study or regarding participants during the study period, and they will be in a position to recommend suspension or ending the trial depending on the severity of the adverse event.

48. Input from Public Involvement Group

Active involvement of People with Lived Experience (PWLE) of SMI is essential for this study. Development of an acceptable and feasible complex intervention requires coproduction with service users and clinicians as well as researchers (MRC, 2008). PWLE has been and will continue to be integrated into all stages of the study (design, development and training for intervention, decisions about outcome measures, recruitment, analysis, and dissemination. We have PWLE representation on the Trial Management Group (co-applicant [name]). We have a group of 4 PWLE who are experienced researchers and trainers as well as having "lived experience" of mental health service use who will act as a PPI advisory group. A PPI consultation event on sexual health and SMI in April 2015 provided the opportunity to engage with a larger and more diverse pool of people for the study. Additionally, the research team will have engaged the NHS service users in each site to participate in focus groups for the development of the intervention. A PWLE support protocol, clearly defining roles, responsibilities and remuneration (in line with INVOLVE guidance) has been developed. [name] (London) and [name] (Huddersfield) will supervise the PWLE consultants and training and support will be provided through the University of Huddersfield.

49. Financing and insurance

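### Read literally, Protocol section 46 reports an event onward only if the team and the DMEC both call it related, so a DMEC-only judgement has no stated route to the sponsor or ethics committee

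*Protocol*

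**What the plan says.** Section 46 (Safety and Adverse events) has all adverse events, serious or not, reported to the Chief Investigator and reviewed under a study-specific SOP by a clinical psychologist at the University of Huddersfield. It notes that relatedness can be hard to judge here and gives this as the reason why "all serious adverse events (SAE) will be forwarded to the DMEC within 48 hours of the CI becoming aware of the event". The next sentence sets the onward step. What goes to the sponsor, ethics committee and TSC is "Any event deemed by the team and the DMEC as 'related' to study treatment".

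On who makes the two judgements, section 23.1 states that "blinding of the participants, clinicians and the researchers is not possible"; only those analysing the data are blind. Section 47.4 describes DMEC members as experts "who are independent of the principal investigator and the study team".

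Three places describe what the DMEC or its Chair is told:
- The adverse-events paragraph of section 46 applies when a participant "needs to be admitted as an inpatient or other adverse event occurs (self-harm, suicide attempt, violence to others or victim of violence". The Chair is to hear within 48 hours.
- The following paragraph of section 46 covers serious adverse events, as quoted above.
- Section 47.4 says "The Chair of the DMEC will be informed of any adverse events that arise from the study or regarding participants during the study period". It gives no time limit.

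**The concern.** The protocol brings in an independent body because the relatedness judgement is difficult, then words the reporting rule so that this body's judgement does not suffice on its own. The two parties are not equally placed. The researchers and clinicians know the allocation, the Chief Investigator supervises the interventionists (section 44), and the event reviewer works at the sponsoring university. The DMEC stands outside all of this. If they differ on whether, say, an assault or a self-harm episode is linked to the intervention, the sentence as worded sends nothing to the sponsor or the ethics committee. Such events are foreseeable. The background section describes raised exposure to partner violence in this population, and section 46 itself expects that survivors of abuse may be distressed by taking part.

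**Working it through.** No arithmetic applies, and the plan gives no figure to reproduce. The check is of the rule's logic and of the other routes in the protocol.

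**Step 1. The relatedness sentence under its two possible readings.**

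| Team's judgement | DMEC's judgement | Reported if both must agree | Reported if either suffices |
|---|---|---|---|
| related | related | yes | yes |
| not related | related | no | yes |
| related | not related | no | yes |
| not related | not related | no | no |

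The readings differ in two of the four rows, which are exactly the rows of disagreement. Under the literal reading each party holds a veto over this report: the team can block the DMEC's *related*, and the DMEC can block the team's.

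**Step 2. Other stated routes for a judgement of relatedness made by the DMEC alone.**

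| Recipient named in section 46 | Other route in the protocol |
|---|---|
| TSC | Yes. Section 47.3 has the DMEC report to the TSC as necessary. |
| Sponsor | None stated. |
| Ethics committee | None stated. Section 47.2 has the Trial Management Group report to the ethics committees on progress, completion, termination or discontinuation. That is trial-level reporting by the trial's own management, not a route for a DMEC judgement on one event. |

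The Chair's powers over the trial (authority to terminate in section 46, a position to recommend suspension or ending in section 47.4) are actions on the whole study. They do not report a single related event to anyone.

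**Step 3. The three descriptions of what the DMEC receives.**

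| Place | Events | Recipient | Clock |
|---|---|---|---|
| Section 46, adverse-events paragraph | Inpatient admission, or another adverse event with a bracketed list; no seriousness test | Chair | 48 hours |
| Section 46, next paragraph | All serious adverse events | DMEC | 48 hours from the Chief Investigator's awareness |
| Section 47.4 | Any adverse event | Chair | None given |

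They differ in scope, recipient and clock. One team could comply with all three at once, so this is a matter of alignment and not a demonstrated contradiction. The sentence on non-serious events at the end of section 46 is cut off in the available copy, so nothing is inferred from it.

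**The case against.** The strongest reply is that the DMEC is far from powerless. Serious events go to it regardless of the team's view, it can report to the TSC without the team's agreement, and its Chair can terminate the trial or recommend ending it. All of this stands. A reader might infer from the sentence that the unblinded team can override the DMEC, or that an event it disputes is never reported onward. The documents do not support that: the effect is confined to this one reporting step, the TSC can be reached another way, and the veto runs in both directions.

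A second reply is that the wording may simply mean events that either body deems related, or that the SOP, which is not shown, settles disagreement. Both are possible. But a sentence that careful staff could apply in opposite ways needs correcting on either reading, and if the SOP has a rule the protocol should match it.

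On notification to the DMEC, a reader might infer that section 46 forwards serious events only and that the sites will therefore notify different sets of events. Neither follows. Section 46 does not say *only*, its sentence on non-serious events is incomplete in this copy, and all adverse events go first to the Chief Investigator, so the sites are not asked to choose what the DMEC sees.

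**Conclusion.** The point holds in a limited form. On the literal reading, an event that only one party calls related is not reported under the relatedness sentence, and a DMEC-only judgement has no stated route to two of the three named recipients, the sponsor and the ethics committee. That sits badly with the protocol's own reason for involving the DMEC. The conclusion rests on the literal reading of one conjunction and on the absence of any disagreement rule in the protocol; it would fall away if the SOP already lets either judgement suffice. No rate of missed reports can be given, because the documents contain nothing on how often the two bodies would differ. The differences between the three notification descriptions are secondary. So is the contrast between a Chair who may terminate (section 46) and one who may recommend ending (section 47.4), which also needs reconciling.

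**What to change.** In the relatedness sentence of section 46, replace the conjunction so that an event deemed related by the team *or* by the DMEC is reported to the sponsor, ethics committee and TSC, and require both judgements to be recorded with the report. Bring the SOP into line.

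In the same amendment, align the two paragraphs of section 46 with section 47.4: one statement of which events go to the DMEC or its Chair, to whom exactly, and by when. The content of that list and its clock are for the sponsor and the DMEC to decide. The two descriptions of the Chair's power should be reconciled at the same time.

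The main change is one conjunction plus a recording requirement; the alignment touches a few sentences. The downside is a few more onward reports of events later found unrelated. Design, sample size and analysis are unaffected.

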22.1 Treatment Allocation

Patients who fulfil the eligibility criteria, who provide written consent to take part in the study and provide baseline data will be eligible for randomisation. Randomisation, will be on a 1:1 basis using stratified block randomisation with stratification by centre and variable block sizes. Patients will be randomised by remote computer to either the sexual health intervention or TAU. This will be conducted using the remote secure randomisation service at York Trials Unit. This will be available as a web-based system (24 hours) and a telephone system (09:00 to 17:00, Monday to Friday, excluding Bank Holidays).

The following information will be collected at randomisation:

- Centre;
- Patient details including full name, gender, date of birth, NHS number, full postal address, contact telephone number(s) and email address;
- Confirmation that patient meets all the eligibility criteria;
- Confirmation that written informed consent has been obtained;
- Confirmation that all baseline data has been collected;
- Confirmation if they can be contacted for future studies.

23. Blinding

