25.2 Follow up data collection

Participants will be followed for a total of 24 weeks. Follow up data collection will be conducted at 3 months (12 weeks) and 6 months (24 weeks) post-randomisation for both groups. We will operate strict "windows" for data collection. At three-month follow-up data collection window will operate from the start of week 11 to the end of week 14. If data is not collected within that time period, this is not pursued and the next time point will be focused on. The 6 month follow-up data collection window will operate from the start of week 23 to end of week 26.
Members of the RESPECT research team will arrange face to face appointments with participants; during these appointments the researchers will collect follow up data covering the main and secondary outcome measures.

The researchers will record missed appointments, as well as how many times they contacted (by text, phone or via case managers) to arrange follow-ups.

26. Qualitative data

There will also be qualitative interviews to gather data on acceptability and feasibility from the perspective of the participants using a sub-sample of consenting participants (see section 13)

27. Data related to fidelity to the intervention

At the end of each session, a short form will be completed by the clinicians delivering the intervention. This will list the content of the session with the clinician ticking what was covered during the session and space to make any additional notes or observations. In addition the participant will be invited to complete a very brief evaluation form.

28. Table of data collection schedule

Event	Time period	Data collected
Pre	Day 0	Consent for study; Baseline CRF:
		Feedback form for refusers

		Randomisation: including confirmation of consent; contact details; confirmation of baseline questionnaire completion
1	1-2 weeks	Intervention participants – First appointment: time of session; the length of session; participant attendance; therapist involved; location; and any materials used.
		Audio recording of sessions
2-6	2-12 weeks	Intervention participants subsequent appointments: time of session; the length of event; participant attendance; therapist involved; location; any materials used.
		Audio recording of sessions.
3	12 weeks	Three month CRF: follow-up.
4	24 weeks	Six month CRF: follow-up. Exit questionnaire

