47.2 Trial Management Group (TMG)

Regular meetings of a Trial Management Group (TMG) will take place to oversee the progress of the trial and review recruitment; the TMG will also be responsible for overseeing the qualitative components of the study. This group will include all co-applicants, collaborators, local principal investigators, representatives from the data management staff, trial statisticians and research staff. The trial will be managed on a day-to-day basis by the York Trials Unit team. The group will meet every two months by either face to face or by an online meeting tool. The group will provide timely reports on the progress, or completion, termination or discontinuation of the study to the ethics committees.

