47.3 Trial Steering Committee (TSC)

The committee will consist of the principal investigators of the study (the co-applicants), an independent chair and at least two other independent members (including PPI team input and independent person with lived experience). The steering group will meet on at least annual basis (at least twice during the study) to discuss progress of the trial, or more often as appropriate. The DMEC, research team and statisticians will report to the TSC as necessary. Meetings for the TSC will alternate between London and University of Huddersfield/York.

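### Section 46 passes a serious adverse event to the sponsor and ethics committee only if it is related to study treatment, which on a literal reading omits serious events caused by research assessments or interviews

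*Protocol*

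**What the plan says.** Section 46 sets up several layers of safety reporting.

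- All adverse events, serious or not, go to the Chief Investigator and are reviewed by a clinical psychologist under a study-specific SOP.
- All serious adverse events go to the DMEC within 48 hours of the Chief Investigator learning of them, whatever their cause.
- Inpatient admission, self-harm, a suicide attempt, and violence by or against the participant go at once to the Chief Investigator or a delegated clinician, and to the DMEC Chair within 48 hours.
- The step beyond the DMEC depends on causality. An event that the team and the DMEC deem related "to study treatment will be reported to the sponsor, ethics committee and TSC".

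The surrounding text uses wider terms. The distress rule in section 46 applies to distress "during any study related activity (e.g. meeting with a member of research team or during intervention delivery"). The stopping rule there reads: "The Chair of the DMEC will have the authority to terminate the trial should there be evidence that the study is causing harm". Section 45.3 states: "The main risk from participating in the study is embarrassment regarding collecting data about sexual behaviour", and adds discussion of sexual health for those receiving the intervention. Section 47.4 has the DMEC Chair told of adverse events that arise from the study or concern participants during it.

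**The concern.** The protocol foresees that taking part, and not only the intervention, can cause harm. Section 46 notes that people who have experienced sexual abuse or exploitation may find participation distressing. The questionnaires ask about sensitive matters, including sex trading and sex under the influence of drugs (section 7), in a population that section 1 describes as having high levels of exploitation and violence.

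Yet the trigger for telling the sponsor and ethics committee about an event is tied to treatment alone. If a participant harmed themselves or was admitted after a distressing assessment, and the team and DMEC judged the assessment to be the cause, the rule as worded would not send that event to either body. At stake is who is told about harm caused by the research itself. No estimate or analysis is involved.

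**Working it through.** The protocol gives no event rate, so no event count can be computed. The check is whether any section supplies the route that section 46 leaves out.

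**Step 1: which research procedures fall outside study treatment?**

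- Baseline assessment. Section 22.1 says that patients "who provide written consent to take part in the study and provide baseline data will be eligible for randomisation", and section 18 lists the baseline assessment before the call to randomise. An event it causes cannot be related to study treatment in any participant.
- Follow-up assessments. Section 25.2 has them "conducted at 3 months (12 weeks) and 6 months (24 weeks) post-randomisation for both groups". An event caused by the assessment is not caused by treatment in either arm. In the TAU arm there is no study-delivered treatment to which it could be related.
- Qualitative interviews. Section 35 plans about 20, ten from each arm.

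**Step 2: how many people does the wording touch?**

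- Scheduled assessments per participant: baseline + 3 months + 6 months = 3, of which 1 precedes randomisation.
- Planned participants: 100, all with a baseline assessment.
- TAU participants at 1:1: 100 / 2 = 50, with assessments but no study sessions.

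These counts describe exposure to the procedures. They do not measure how many events would be missed.

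**Step 3: is there another route for a serious event caused by a research procedure?**

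| Section | Who is told, and of what | Event-level route to sponsor or ethics committee? |
|---|---|---|
| 46, distress rule | Supervision; the Chief Investigator or delegated clinician within 24 hours if the participant is referred | No |
| 46, listed events and SAEs | Chief Investigator, DMEC or its Chair | No |
| 46, related events | Sponsor, ethics committee, TSC | Yes, but only if related to study treatment |
| 43 and 45.1 | General commitment to GCP and regulatory requirements | None stated |
| 47.2 | "The group will provide timely reports on the progress, or completion, termination or discontinuation of the study to the ethics committees" | No; these are study-level reports |
| 47.3 | "The DMEC, research team and statisticians will report to the TSC as necessary" | No; TSC only |
| 47.4 | DMEC Chair, adverse events | No |

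The only event-level route to the sponsor and ethics committee is the one restricted to study treatment.

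**Step 4: can the term be read broadly?** Section 46 itself distinguishes meeting a researcher from delivering the intervention when it describes study-related activity, and refers to the study when it sets the stopping rule. Where the authors wanted the wider scope, they wrote it. A reader applying the reporting rule would reasonably take the narrower term as meant.

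**Step 5: the DMEC Chair's powers.** Section 46 gives the Chair authority to terminate, on evidence that the study is causing harm. Section 47.4 lets the Chair recommend suspension or ending, according to how severe the event is. Each power has its own condition. Neither section says what happens when both conditions are met, or whether the Chair's word is then final.

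**The case against.** The strongest case against is that little is lost in practice. Every serious adverse event goes to independent review by the DMEC whatever its cause, which is the protocol's own answer to the difficulty of judging relatedness. The adverse event reviewer works at the University of Huddersfield, which is also the sponsor. The study is bound to GCP. The SOP, which is not shown, may define relatedness more broadly. If harm led to termination, the ethics committees would be told under section 47.2.

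Much of this stands, and it is why the point is minor. It does not close the gap. Having a reviewer at the sponsor's institution is not notification of the sponsor, the GCP commitment names no route for an event, and an SOP should not have to correct a criterion fixed in the protocol.

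Three stronger readings are tempting, and the document does not support them.

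- A reader might infer that harm from assessments goes unreported. It does not: the Chief Investigator and the DMEC receive serious events regardless of cause, and the TSC may hear as necessary.
- A reader might extend the gap to all adverse events. The sentence that opens on non-serious events breaks off in the available text, so their route is unknown and nothing can be claimed about them. Embarrassment, named in section 45.3, is in any case not a reportable event.
- A reader might say that sections 46 and 47.4 contradict each other without saying when each power applies. They do attach conditions (evidence of harm in one, event severity in the other) and can be read together. Only the finality of the Chair's decision is unclear.

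**Conclusion.** The concern holds for serious adverse events only. As worded, section 46 gives no event-level route to the sponsor or ethics committee for a serious event caused by the baseline assessment, a follow-up assessment in either arm, or a qualitative interview. The trigger is narrower than the protocol's own stopping rule and distress rule.

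The severity is minor. The number of events affected is unknown, independent review by the DMEC is already in place, and the sample size and descriptive results are untouched. The conclusion assumes that study treatment carries its ordinary meaning (the sexual health intervention or usual care) and that neither the SOP nor the lost text widens it for serious events. The uncertainty over whether the DMEC Chair's decision is final is a smaller, separate point of governance.

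**What to change.** In section 46, change the reporting trigger to: *related to study treatment or to any study procedure, including assessments and qualitative interviews*. Use the same wording in the adverse event SOP.

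Add one sentence, consistent across sections 46 and 47.4, saying whether the DMEC Chair's decision to stop is final or advisory. If it is advisory, the recommendation should go for decision to the TSC, to which the DMEC already reports under section 47.3, and to the sponsor.

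Both are wording edits that fit a minor amendment. They need no extra participants, visits or data. The downside is at most a few more event reports to the sponsor, ethics committee and TSC.
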